## 6.4.1 Dose Modification

No dose modifications are permitted on a patient-basis in this study. Dose interruptions are required in case of DILI, anemia, and hypothyroidism, when the events meet the

criteria as defined in Appendix II, Section 5.3.2.2, and Section 5.3.2.3, respectively. Events that require permanent discontinuation of IMP are listed in Section 4.4.1.

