9.6.4 Per Protocol Analysis Set

Per Protocol analysis set (PPS) comprises of all subjects in the FAS who do not have any important protocol deviations during the 24-week treatment period that would potentially affect the efficacy of the study drug. Subjects will be analyzed based on the treatment group they were randomized to regardless of the actual treatment received.

Important protocol deviations are defined in the Protocol Deviation Guidance Document for the study. Prior to database lock and unblinding of the study, a blinded data review of the important protocol deviations (including programmatically determined deviations) will be performed to identify the important deviations impacting on the efficacy endpoints. This analysis set will be defined in a blinded manner prior to unblinding the study and agreed with Sponsor.

Deviations impacting efficacy that may lead to exclusion from the PPS will include:

- Deviations related to inclusion/exclusion criteria
- Incorrect treatment received (i.e. the actual treatment received is different to the initially randomized treatment at any point during the first 24-weeks of treatment)
- Non-compliance with study drug intake (≤80%) during the first 24-weeks of treatment
- Efficacy assessments at Week 24 performed significantly out of the protocol specified window
- Missing baseline data for the primary endpoint
- Use of prohibited concomitant medication that could have impacted the efficacy of study treatment.

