10.4 Dates of First and Last Dose of Study Drug

The date of first dose of IMP will be the first dose date recorded on the Study Drug page of the CRF. The date of the first dose of IMP in the Extension Phase, will be the first dose date on the Study Drug Administration (Extension Phase) page of the CRF.

If no date of first dose of IMP is available and the subject was not treated, date of first dose of IMP will be missing and the date of randomization will be used in any calculations requiring treatment start date.

Date of last dose of IMP will be the date collected as the completion/discontinuation date on the End of Treatment page of the CRF. If date of last dose of IMP is not available and subject is lost to follow-up based on End of Treatment CRF page, date of last scheduled visit or date of last telephone contact where a dose is recorded, will be used as the date of last dose of IMP.

Subjects who entered the Extension Phase under protocol versions 1.0 to 4.0 will have no End of Treatment page completed after completion of the randomized part. For these subjects, date of the last dose of IMP in the randomized part will be the day prior to the date of the first dose of IMP in the Extension Phase.

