10.7 Adverse Events

10.7.1 Treatment Period

The analysis of safety assessments over the **24-week treatment period** (Week 24 + 30 days) will be conducted:

- For patients enrolled under protocol version 5.0 or later who complete the 24-week treatment period, a Week 28 (EoT) visit will occur 30 days after the date and time of last dose of IMP. All safety data will be analyzed.
- For patients enrolled under protocol versions 1.0 to 4.0, treatment may have continued beyond Week 24. Regardless, the safety data will be cut at Week 28 (Week 24 + 30 days) to ensure a consistent safety follow-up period for all patients.

This approach enables the evaluation of the safety and tolerability of setanaxib over a 24-week treatment period, consistent with the study objectives.

The analysis of safety assessments over the **52-week treatment period** (Week 52 + 30 days) will also be conducted:

- Patients enrolled under protocol version 5.0 will contribute safety data up to Week 28 only. All safety data will be analyzed.
- For patients enrolled under protocol versions 1.0 to 4.0 who complete the 52-week treatment period and do not enter the extension phase, a Week 56 (EoT) visit will occur 30 days after the date and time of last dose of IMP. All safety data will be analyzed.
- For patients enrolled under protocol versions 1.0 to 4.0 who entered the extension phase, the safety data will be cut at Week 56 (Week 52 + 30 days) to ensure a consistent safety follow-up period for all patients.

This approach enables the evaluation of the safety and tolerability of setanaxib over the whole randomized treatment period and provides longer-term safety information. This approach will be applied to other safety endpoints.

Note: For the analysis of study drug exposure and compliance (Section 12.3.3), the last dose of IMP in the 24-week treatment period will be cut at week 24, and the last dose in the 52-week treatment period (for subjects who received more than 24 weeks of treatment) will be cut at week 52. "+ 30 days" will not be considered in the drug exposure and compliance.

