12.3.3 Extent of Study Drug Exposure

The extent of exposure will be characterized for the SS according to the number of subjects who received at least one dose, the total number of doses received, the duration of therapy (weeks), duration of interruptions, the reasons for interruptions and study drug compliance. The summaries will be repeated for each treatment period, as defined in Section 10.7.1.

At each dispensing visit, subjects will be dispensed kit(s) comprising of 4 bottles containing 70 tablets each. Subjects are expected to take 4 tablets per day, 1 tablet from each bottle, 2 in the morning, 2 tablets in the evening.

The duration of exposure, regardless of temporary interruptions, will be defined as the

$$Duration (weeks) = \frac{(Last dose of IMP - First dose of IMP) + 1}{7}$$

The date of last dose of IMP in the 24-week treatment period and date of last dose in the 52-week treatment period (for subjects who received more than 24 weeks of treatment), respectively will be used in the above derivation. For the Extension Phase, the date of last dose of IMP in the Extension Phase will be used in the extension phase will be used in the above derivation and this data will be listed only.

During the course of the study, the dose may be interrupted due to safety concerns. The start date and end date of the interruption will be recorded on the Dose Interruptions page of the CRF. The number of subjects with an interruption at any point of the study will be summarized and the duration of interruption will be calculated as:

$$Duration \ of \ Interruption \ (weeks) = \frac{(End \ Date \ of \ Interruption - Start \ Date \ of \ Interruption) + 1}{7}$$

The reasons for the interruption will also be presented. If a subject has multiple interruptions during the study period, all individual interruptions will be summed to determine the overall period of treatment interruption.

The total number of doses administered will be calculated using values from the Drug Accountability CRF form and will be defined as:

 $Total\ Number\ of\ Doses\ Administered = Sum\ of\ no\ of\ doses\ dispensed - Sum\ of\ no\ of\ doses\ returned$

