With the doses dispensed at a visit calculated as the number of bottles dispensed at a visit multiplied by the amount of tablets per bottle dispensed (70 tablets per bottle). The number of doses returned at a visit will be the sum of all tablets returned per bottle. If at a visit the number of doses returned for a bottle is missing, it will be assumed that the subject used the full amount of tablets in a bottle i.e. 0 will be used as the returned amount in the calculation. The total number of doses administered will be summarized for the Main Part. Extension Phase and Overall.

The compliance to study drug will also be calculated as:

Sponsor: Calliditas Therapeutics Suisse SA

Protocol No: GSN000350

 $Compliance~(\%) = 100* \frac{Total~Number~of~Doses~Administered}{Expected~number~of~tablets~to~be~taken}$

The expected number of tablets to be taken will be estimated based on the duration of exposure and defined as:

(Date of last dose in the period of interest – date of first dose in the study +1) X 4 tablets/day

The following compliance categories will also be displayed: <75%, ≥75 to <90%, ≥90%, 100%. Compliance and total number of doses administered will be calculated for the SS (by treatment period defined in Section 10.7.1) and Extension Phase (where applicable), where expected number of tablets will be the expected number during each reporting phase and total number of doses administered the number administered during each phase.

Study drug accountability, study drug compliance and interruptions will be listed.

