12.5.2.3 Supplementary Analyses

If there are important protocol deviations that impact efficacy, the primary analysis (see Section 12.5.2.1) will be repeated using the PPS. Subjects with important protocol deviations could falsely draw the estimated treatment difference closer. Exclusion of these subjects in this sensitivity analysis will help assess the magnitude, if any, of this effect.

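### The Per Protocol compliance cut counts tablets only up to the last dose, so a patient who stops for good at Week 2 can score 100% while one who takes 75% of 24 weeks is flagged

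*SAP*

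**What the plan says.** SAP 9.6.4 defines the PPS as FAS patients without important deviations bearing on efficacy. One listed deviation that may lead to exclusion is "Non-compliance with study drug intake (≤80%) during the first 24-weeks of treatment". The others are eligibility, wrong treatment, a Week 24 assessment well out of window, missing baseline and prohibited medication. Neither SAP 9.6.4 nor Protocol 8.2 lists early stopping of drug or a minimum exposure.

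SAP 12.3.3 gives the only compliance formula: tablets taken divided by tablets expected. On the denominator it says "The expected number of tablets to be taken will be estimated based on the duration of exposure", written out as "Date of last dose in the period of interest – date of first dose in the study +1) X 4 tablets/day". Duration of exposure is defined there without subtracting interruptions.

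The last-dose date is set in SAP 10.4: "Date of last dose of IMP will be the date collected as the completion/discontinuation date on the End of Treatment page of the CRF". SAP 10.7.1 adds that "the last dose of IMP in the 24-week treatment period will be cut at week 24", which shortens longer treatment but does not extend the period for someone who stopped early.

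Protocol 6.4.1 states: "Dose interruptions are required in case of DILI, anemia, and hypothyroidism", subject to criteria given elsewhere in the protocol. SAP 12.5.2.3 repeats the primary analysis on the PPS because "Subjects with important protocol deviations could falsely draw the estimated treatment difference closer".

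**The concern.** The rule does not rank patients by how much drug they took. Permanent stopping cannot lower the score, because the denominator stops with the patient. A gap in dosing followed by resumption does lower it.

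This matters because patients who stop drug are asked to continue to Week 24, and under SAP 12.5.2 their Week 24 ALP is used unless they have started new PBC medication. Those values enter the FAS by design, under a treatment policy strategy. If the same patients also pass into the PPS, both estimates carry the same off-drug values. SAP 12.5.2.4 plans a forest plot of FAS and PPS side by side. Close agreement would invite a reading of robustness to poor exposure that the comparison cannot support. The problem arises even with complete and correct tablet counts.

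**Working it through.** The SAP gives no worked compliance figure, so there is none to reproduce. The check applies its formula directly.

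**Inputs**
- Tablets per day: 4 (SAP 12.3.3, "Subjects are expected to take 4 tablets per day").
- Planned treatment: 24 weeks = 168 days, so 168 × 4 = 672 tablets.
- Flag: compliance ≤80% (SAP 9.6.4).
- SAP formula: 100 × tablets taken / [(last dose − first dose + 1) × 4].
- Alternative: 100 × tablets taken / 672.

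**Results**

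| Patient | Tablets taken | SAP 12.3.3 | Against 672 |
|---|---|---|---|
| Full intake, stops at Week 2 | 14 × 4 = 56 | 56/56 = 100% | 8.3% |
| Full intake, stops at Week 4 | 112 | 100% | 16.7% |
| Full intake, stops at Week 8 | 224 | 100% | 33.3% |
| Full intake, stops at Week 12 | 336 | 100% | 50.0% |
| Full intake, stops at Week 16 | 448 | 100% | 66.7% |
| On drug 24 weeks, takes 75% | 0.75 × 672 = 504 | 504/672 = 75.0% | 75.0% |

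Under the SAP formula only the last patient is flagged, although that patient took 504/56 = 9 times as many tablets as the Week 2 stopper. Against 672, all six are flagged.

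**Where the planned denominator draws the line.** 0.80 × 672 = 537.6 tablets, or 134.4 days (19.2 weeks) of full intake. A fully adherent patient who stops before then is flagged.

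**Interruptions.** With otherwise perfect intake to Week 24, the flag is reached at 0.20 × 168 = 33.6 days off drug. At 34 days the score is (168 − 34)/168 = 134/168 = 79.8%. Changing the denominator to 672 leaves this unchanged (536/672 = 79.8%). Taking those days out of the denominator gives 536/(134 × 4) = 100%. Interruptions therefore need their own rule.

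**Time off drug.** A patient whose last dose is on Day 14 and who attends Week 24 on Day 169 gives an ALP value 155 days, about 22 weeks, after the last dose.

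**The case against.** The best defence is that the PPS is built on protocol deviations, and stopping when the protocol says to stop is not one. Protocol 4.4.1 directs discontinuation for suspected liver injury, QTc prolongation, confirmed hypothyroidism, pregnancy and other reasons. SAP 12.5.2 treats deviations and treatment discontinuation as separate intercurrent events. A PPS that keeps patients who obeyed the stopping rules is coherent, and SAP 12.5.2.3 does not promise a completers' analysis.

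That would be a sound position if the rule followed it. It does not: interruption days, which the protocol also requires in some cases, remain in the denominator and count against the patient. The rule fits neither a deviations-only aim nor a minimum-exposure aim.

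A second objection is that SAP 9.6.4 does not cross-refer to 12.3.3, that the categories in 12.3.3 have no 80% cut, and that the 24-week phrase could mean the full planned period. SAP 12.4 reports that the ≤80% deviation was derived by program and agreed at blinded review, without giving its denominator. So the derivation used may differ from 12.3.3. But no other formula is written, so at the least the denominator needs stating.

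Third, exclusion is not automatic. Listed deviations may lead to it, the set is settled at blinded review, and the Protocol Deviation Guidance Document is not among the documents reviewed. A stopper could also leave the PPS on another listed ground. All of this stands and limits how firmly the result can be put.

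**Conclusion.** The point holds as a defect in a supplementary analysis. As written, the compliance criterion cannot identify a patient with full intake who stops early, and no other listed criterion is aimed at that patient. PPS agreement with the FAS would be uninformative about dilution from early stopping. The FAS estimate, its p-values and the Hochberg test are untouched. The 100% score assumes full intake up to the stop date.

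Two stronger readings are tempting and are not supported.

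- A reader might infer that the protocol requires interruptions long enough to trigger exclusion. The 34 days is back-calculated from the 80% cut. No section sets such a duration; retests are due within 7 days for anemia (Protocol 5.3.2.2) and within 5 days for TSH (5.3.2.3), and the total time to resumption is not given.
- A reader might turn the assumed 25% dropout into a dilution figure: with 5 of 22 per active arm returning off drug with no residual effect, the planned difference of 25 − 2.5 = 22.5 points becomes 22.5 × 17/22 = 17.4. But that 25% takes 22 enrolled to about 16 evaluable per arm (22 × 0.75 = 16.5), so it counts patients lost to evaluation, not stoppers who come back. The documents give no number for the latter, so the size of any dilution is unknown.

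**What to change.** Before unblinding, amend SAP 9.6.4 for the PPS criterion only:

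1. Compute compliance against the planned 24-week supply: 168 × 4 = 672 tablets, or 4 × planned days to the Week 24 visit.
2. State separately whether documented protocol-required interruption days are taken out of the denominator.
3. Keep the exposure-based figure in the descriptive table of SAP 12.3.3.
4. Show by arm how many patients each definition excludes, and give the PPS estimate under both.

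The cost is a short amendment and a re-derived flag. Because SAP 12.4 says the existing flag was already agreed, the change must go back through blinded review. If it is made after unblinding, it should be labelled post hoc.

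The downside is a smaller PPS that also removes patients who stopped as the protocol directs. That removal may be uneven by arm: Protocol 1.1.4 reports four liver SAEs considered possibly related and one QTc SAE, all with drug discontinued and the arm not stated. The revised PPS is selected on a post-randomisation event, as any per-protocol set is, and should be read only as supplementary. If the intention is to keep early stoppers in the PPS, the SAP should say so and should not present FAS–PPS agreement as evidence about early stopping.

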12.4 Important Protocol Deviations

Per ICON processes, protocol deviations data will be entered into the ICON system of record (PSO), in accordance with the Protocol Deviation Guidance Document. Important protocol deviations are defined in the protocol deviation guidance document. The final approved version of protocol deviation guidance will be finalized before the database lock for the primary analysis. The study team and the Sponsor will conduct on-going reviews of the deviation data from PSO, adjusting the deviation criteria as seems appropriate.

Protocol deviation data will be reviewed prior to database lock and important deviations with a potential impact on efficacy leading to the elimination of subjects from the PP will be identified. The PP must be finalized at the blinded data review meeting (or earlier), prior to database lock for the primary analysis and agreed with the Sponsor.

During the blinded data review meeting that was conducted prior to database lock, it was identified that several important deviations with impact on efficacy per section 9.6.4 were not entered into PSO. As such, programmatic PDs for deviations related to inclusion/exclusion criteria and non-compliance with study drug intake (≤80%) were derived and agreed in the blinded data review meeting and subsequently used as an additional protocol deviation source for analysis.

The number of subjects with important protocol deviations will be summarized in the FAS by category of violation and by treatment group including subset of Important protocol deviations leading to exclusion from the PP. For the primary analysis, all protocol deviations will also be listed. Deviations that occurred over a 24-weeks treatment period, over a 52-weeks treatment period and occurred during the extension phase will be flagged in the listings.

12.5 Efficacy Analyses

12.5.1 Hypothesis Testing Strategy and Multiplicity

The objective of the primary efficacy analysis will be to evaluate the efficacy of setanaxib versus placebo in the treatment of subjects with PBC and elevated liver stiffness. The aim of the efficacy analysis is to demonstrate superiority of setanaxib over placebo.

The null hypothesis is no difference in change in ALP (%) between setanaxib and placebo over 24 weeks. The alternative hypothesis is that setanaxib demonstrates a difference in change in ALP (%) over placebo.

To control the study-wise error rate, that is, the probability of rejecting the true null hypothesis for the primary endpoint at 1-sided 0.025, a Hochberg step-up procedure will be applied to adjust for 2 dose comparisons versus placebo. The hypothetical example below is used to illustrate the procedure.

• The primary analysis will be performed and the p-values for each setanaxib dose versus placebo will be assigned a rank (#1 for the smallest p-value and #2 for the largest p-value).

Sponsor: Calliditas Therapeutics Suisse SA

Protocol No: GSN000350

• Next, the Benjamini-Hochberg (BH) critical value will be calculated for each p-value, using the formula: (i/m)*Q where *i* = rank of p-value (1 or 2), m is the number of tests (this will be set to 2) and Q is the false positive risk (this will be set to 0.025, for a 1-sided test). Thus, the p-value with Rank 1 will have a BH critical value of 0.0125 and the p-value with Rank 2 will have a BH critical value of 0.025.

Example

Example				
Comparison	Hypothetical observed P-value	Rank	BH-critical value (i/m)*Q	
1. Setanaxib 1600mg vs placebo	0.020	1	0.0125	
2. Setanaxib 1200mg vs placebo	0.024	2	0.025	

• The test with the largest p-value that is less than its Benjamini-Hochberg critical value is comparison #2. This test and all tests with a smaller p-value will be considered significant. Therefore, in this hypothetical example, both dose comparisons will be deemed statistically significant.

For the analysis of secondary and exploratory endpoints, multiplicity will not be adjusted. "Nominal" p-values will be presented and will not be considered as part of the study-wise control of type I error. This is considered appropriate for an exploratory Phase 2b study.

12.5.2 Primary Estimand

For the primary efficacy analysis, each setanaxib treatment group (1600 mg and 1200 mg) will be compared with placebo. The primary estimand is to assess the change in ALP (%) over 24 weeks in subjects with PBC, elevated liver stiffness, and intolerance or inadequate response to UDCA.

The intercurrent events of Important protocol deviations impacting efficacy and treatment discontinuation prior to Week 24 for any reason not considered under the Composite Strategy (below) will be handled with a treatment policy strategy (the primary estimand) and the value recorded for the variable of interest is used regardless of whether or not the intercurrent event occurs (ICH E9 R1 addendum). The intercurrent events of starting additional PBC-related medications after randomization and prior to Week 24 or death prior to week 24 will be handled with a composite variable strategy, where efficacy data collected following the intercurrent event will be excluded from the primary analysis. PBC-related medication(s) will be identified through blinded medical review prior to database lock.

Table 6: Definition of Intercurrent Events

Intercurrent Event	Strategy	Comment
Important protocol deviations that impact efficacy	Treatment policy strategy	The occurrence of the intercurrent event is considered irrelevant in defining the treatment effect of interest, the value for the variable of interest is used regardless of whether or not the intercurrent event occurs
Starting additional PBC-related medications after randomization and before Week 24 Death before Week 24	Composite variable strategies	Efficacy data collected after these events will be excluded from the primary analysis.

